11. DESCRIPTION OF GLOBAL AMENDMENT(S)

[figure not shown]
11.1 GLOBAL AMENDMENT 1

Date of amendment	10 Feb 2020
EudraCT number	2019-003389-42
EU number	
BI Trial number	1399-0013
BI Investigational Medicinal Product(s)	BI 1265162
Title of protocol	Investigation of metabolism and pharmacokinetics of BI 1265162 (C-14) after intravenous administration (Part 1) and investigation of metabolism and pharmacokinetics of BI 1265162 (C-14) after oral administration (Part 2) in healthy male subjects following a non-randomized, open-label, single-dose, single arm per trial part mass balance design
To be implemented only after approval of the IRB / IEC / Competent Authorities	
To be implemented immediately in order to eliminate hazard – IRB / IEC / Competent Authority to be notified of change with request for approval	
Can be implemented without IRB / IEC / Competent Authority approval as changes involve logistical or administrative aspects only	
Section to be changed	Synopsis Flow Chart 1 and foot note 9 Flow Chart 2 and foot note 10 Section 1.2.5 Section 2.2.2.3 Section 3.3.3 Section 5.2.3, Table 5.2.3: 1 Section 5.3.2.1 Section 5.3.2.2
Description of change	Correction of typographical and factual errors as well as inconsistencies
Rationale for change	Correction of typographical and factual errors as well as inconsistencies

Proprietary confidential information © 2020 Boehringer Ingelheim International GmbH or one or more of its affiliated companies

11.2 GLOBAL AMENDMENT 2

Date of amendment	25 February 2020
EudraCT number	2019-003389-42
EU number	
BI Trial number	1399-0013
BI Investigational Medicinal Product(s)	BI 1265162
Title of protocol	Investigation of metabolism and pharmacokinetics of BI 1265162 (C-14) after intravenous administration (Part 1) and investigation of metabolism and pharmacokinetics of BI 1265162 (C-14) after oral administration (Part 2) in healthy male subjects following a non-randomized, open-label, single-dose, single arm per trial part mass balance design
To be implemented only after approval of the IRB / IEC / Competent Authorities	
To be implemented immediately in order to eliminate hazard – IRB / IEC / Competent Authority to be notified of change with request for approval	

2. LIST OF ABBREVIATIONS

See Medicine Glossary:

<http://glossary>

| Term | Definition / description |
|---------------------------|--|
| ALT | Alanine transaminase |
| AST | Aspartate transaminase |
| AUC _{0-tz} | Area under the concentration-time curve of the analyte in plasma over the time interval from 0 to the last quantifiable data point |
| BMI | Body mass index |
| CI | Confidence interval |
| C _{max} | Maximum measured concentration of the analyte in plasma |
| CV | Arithmetic coefficient of variation |
| DBLM | Database lock meeting |
| DILI | Drug induced liver injury |
| fe _{faeces,0-t2} | fraction of (C-14)-radioactivity excreted in faeces as percentage of the administered dose over the time interval from 0 to the last quantifiable time point |
| fe _{urine,0-t2} | fraction of (C-14)-radioactivity excreted in urine as percentage of the administered dose over the time interval from 0 to the last quantifiable time point |
| fe _{vomit,0-t2} | fraction of (C-14)-radioactivity excreted in vomit as percentage of the administered dose over the time interval from 0 to the last quantifiable time point |
| gCV | Geometric coefficient of variation |
| gMean | Geometric mean |
| LLT | Lower level term |
| IQRMP | Integrated Quality and Risk Management Plan |
| iv | intravenous |
| ■ | |
| Max | Maximum |
| MedDRA | Medical Dictionary for Regulatory Activities |
| Min | Minimum |
| N | Number non-missing observations |
| P10 | 10th percentile |

| Term | Definition / description |
|-------------|---|
| P90 | 90th percentile |
| po | Oral |
| PKS | Pharmacokinetic parameter analysis set |
| Q1 | 1st quartile |
| Q3 | 3rd quartile |
| qd | Once daily |
| RAGe | Report Appendix Generator system |
| REP | Residual effect period |
| SD | Standard deviation |
| SOC | System organ class |
| TS | Treated set |
| ULN | Upper limit of normal |
| WHO-DD | World Health Organization Drug Dictionary |

3. INTRODUCTION

As per ICH E9 (1), the purpose of this document is to provide a more technical and detailed elaboration of the principal features of the analysis described in the protocol, and to include detailed procedures for executing the statistical analysis of the primary and secondary variables and other data.

This trial statistical analysis plan (TSAP) assumes familiarity with the Clinical Trial Protocol (CTP), including Protocol Amendments. In particular, the TSAP is based on the planned analysis specification as written in CTP Section 7 “Statistical Methods and Determination of Sample Size”. Therefore, TSAP readers may consult the CTP for more background information on the study, e.g., on study objectives, study design and population, treatments, definition of measurements and variables, planning of sample size, randomisation.

Study data (including data entered in the RAVE EDC system and external data provided by suppliers) will be stored in a Clinical Data Repository (CDR).

Pharmacokinetic (PK) parameters will be calculated using Phoenix WinNonlin™ software (version 6.3 or higher, Certara USA Inc., Princeton, NJ, USA).

The statistical analyses will be performed within the validated working environment CARE, including SAS® (current Version 9.4, by SAS Institute Inc., Cary, NC, USA), and a number of SAS®-based tools (e.g., macros for the analyses of AE data or laboratory data; Report Appendix Generator system (RAGe) for compilation/formatting of the CTR appendices).

4. CHANGES IN THE PLANNED ANALYSIS OF THE STUDY

Recruitment stopped after Part 1 due to COVID-19 pandemic. Before the planned re-start of recruitment into Part 2, the study was prematurely stopped as Boehringer Ingelheim decided not to further develop the compound BI 1265162.

Consequently, only a subset of the analyses planned in the CTP will be performed, and only data from Part 1 (intravenous administration of the compound) will be analysed. For all study endpoints, listings will be provided. Tables will be provided for disposition, demography and adverse events (including one of the secondary endpoints) as well as for mass balance and PK endpoints (including the primary and all further secondary endpoints). For variables regarding medical history, concomitant medication and non-drug procedures, exposition, protocol deviations, laboratory data, vital signs and local tolerability, only listings will be provided and no descriptive analysis will be carried out.

In CTP section 7.3 the following was defined: *Important protocol deviation (iPD) categories will be specified in the Integrated Quality and Risk Management Plan, iPDs will be identified no later than in the Report Planning Meeting, and the iPD categories will be updated as needed.*

Due to SOP changes, the iPD categories are no longer available in the IQRM plan but included in an iPD specification file (3). The iPD categories originally defined in IQRM plan were transferred to the iPD specification file. Minor changes regarding the iPD categories were performed only.

5. ENDPOINTS

5.1 PRIMARY ENDPOINTS

Section 2.1.2 of the CTP:

The following parameters will be determined:

(Part 1 & 2) Mass balance recovery of total (C-14) BI 1265162-radioactivity in urine and faeces (and vomit, if applicable). Amount of radioactivity excreted as a percentage of the administered single intravenous or oral dose of BI 1265162 (C-14) in

- *Urine - $f_{e\text{urine}, 0-tz}$ (fraction of (C-14)-radioactivity excreted in urine as percentage of the administered dose over the time interval from 0 to the last quantifiable time point)*
- *Faeces - $f_{e\text{faeces}, 0-tz}$ (fraction of (C-14)-radioactivity excreted in faeces as percentage of the administered dose over the time interval from 0 to the last quantifiable time point)*
- *Vomit - $f_{e\text{vomit}, 0-tz}$ (fraction of (C-14)-radioactivity excreted in vomit as percentage of the administered oral dose over the time interval from 0 to the last quantifiable time point) - if feasible and appropriate*

The timeframe for determination of these endpoints depends on the time of discharge of each subject, based on radioactivity excretion, and is predicted to vary between 9 and 38 days after drug administration.

5.2 SECONDARY ENDPOINTS

5.2.1 Key secondary endpoints

This section is not applicable as no key secondary endpoints have been specified in the protocol.

5.2.2 Secondary endpoints

Section 2.1.3 of the CTP:

The following parameters will be determined:

(Part 1 & 2) Assessment of the pharmacokinetics of a single intravenous or oral dose of BI 1265162 (C-14) by means of the following parameters for total (C-14) BI 1265162-radioactivity, BI 1265162 and metabolite M582 (1) in plasma:

- *AUC_{0-tz} (area under the concentration-time curve of the analyte in plasma over the time interval from 0 to the last quantifiable data point)*
- *C_{max} (maximum measured concentration of the analyte in plasma)*

(Part 1 & 2) Evaluation of safety and tolerability of a single intravenous or oral dose of BI 1265162 (C-14) by means of

- *Percentage of subjects with drug related adverse events (AEs) including clinically relevant findings from the physical examination*

5.3.3 Safety endpoints

Section 2.2.2.5 of the CTP:

Further safety and systemic tolerability endpoints:

- *Safety laboratory tests*
- *12-lead electrocardiogram (ECG), and*
- *Vital signs (blood pressure [BP], pulse rate [PR])*
- *Physical examination*

Additionally, local tolerability will be assessed in Part 1 with intravenous administration (see CTP section 2.2.2.4).

5.4 OTHER VARIABLES

Section 5.2.1 of the CTP: *At screening, the medical examination will include demographics, height and body weight, smoking and alcohol history (results not mandatory to be entered into CRF or to be reported), relevant medical history and concomitant therapy, review of inclusion and exclusion criteria, review of vital signs (BP, PR), 12-lead ECG, laboratory tests, and a physical examination.*

Age [years] will be determined as the difference between year of informed consent and year of birth.

BMI will be calculated as weight [kg] / (0.01 * height [cm])².

6. GENERAL ANALYSIS DEFINITIONS

6.1 TREATMENTS

For basic study information on investigational products, assignment of treatment and selection of doses, please see CTP, Section 4.

The study consists of 2 trial parts, Part 1 with intravenous administration and Part 2 with oral administration of the study medication. Each part follows a non-randomized, open-label, single-dose, single arm, mass balance design. It was planned that 7 healthy male subjects will enter each trial part, i.e. 14 subjects in total. Subjects will be treated with a single dose of the study medication as outlined in Table 6.1: 1 below.

Table 6.1: 1 Treatments and labels used in the analysis

| Part | Treatment | Short label |
|------|--|-------------|
| 1 | BI 1265162 (C-14) solution for infusion , 5 mcg/mL, 50mcg, iv, qd | BI-C-14 iv |
| 2 | BI 1265162 (C-14) oral solution, 0.25 mg/mL, 5mg, po, qd | BI-C-14 po |

The study was prematurely stopped after Part 1 (intravenous administration of BI 1265162 (C-14)). Therefore, all analyses will be performed for the first part only (n=7).

Section 1.2.6 of the CTP: *The Residual Effect Period (REP) of BI 1265162 is 7 days. This is the period after the last dose with measurable drug levels and/ or pharmacodynamics effects is still likely to be present.*

As the REP refers to the non-labelled BI agent but the investigational drug is radiolabelled, the definition of treatment-emergent AEs will be based on discharge from study site (see CTP Section 7.3.4). According to the study protocol, subjects will be discharged from study site at Day 9 at the earliest. In this discontinued trial, all subjects were discharged from study site at Day 9. Hence, the following study phases will be defined for the analysis of AEs:

- **Screening** (ranging from 0:00 h on day of informed consent until date/time of first administration of study medication)
- **On treatment** (ranging from the first time of administration of study medication until 0:00h on the day after discharge from study site at Day 9)
- **Follow-up (F/U)** (ranging from 0:00h on the day after discharge from study site at Day 9 until 0:00 h on the day after trial termination date)

Section 7.3.4 of the CTP: *Note that AEs occurring after the last per protocol contact but entered before final database lock will be reported to Pharmacovigilance only and will not be captured in the trial database.*

The following AE displays will be provided in the report:

Section 15.3 and Appendix 16.1.13.1.8 (for ClinicalTrials.gov and EudraCT) of the CTR displays:

In these displays, the on-treatment phase will be analysed (labelled with the name of the study treatment (short label)). Screening and Follow-up period will not be included in this analysis. Tables of AEs will present results by the above mentioned on-treatment phase.

In Section 15.4 and Appendix 16.2 (Listings) of the CTR displays, screening and follow-up periods will be included and no totals will be provided.

For detailed information on the handling of the treatments refer to Technical TSAP ADS (analysis data set) plan and Analysis Data Reviewers guide.

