7. All stools (for (C-14) BI 1265162 -radioactivity and metabolic profiling) will be collected quantitatively in portions up to 192 hours (sampling intervals of 0-24, 24-48, 48-72, 72-96, 96-120, 120-144, 144-168,168-192 hours) after administration of BI 1265162 (C-14). Thereafter 24-h collections are to be performed on Days 14-16, 21-23, 28-30, and 35-37. A blank sample will be collected before drug administration on Day -2, Day -1 or Day 1 (see [Section 5.3.2.6](#)). Faeces sampling for (C-14) BI 1265162 -radioactivity assessment will be stopped when the release criteria for radioactivity recovery (see [Section 3.1](#)) have been met (earliest stopping on Day 9). “+” means end of last collection interval, start of following collection interval. For details on sample usage, see [Section 5.3.2.6](#).
8. Measurement of haematocrit and potassium, only.
9. AEs and concomitant therapies will be recorded throughout the trial. At 1:05, 2 , 4 , 8, 24, 48, 192h after the infusion, local tolerability will be assessed according to the criteria put down in [Section 2.2.4](#).
10. End-of-trial (EoT) examination to be performed after last discharge from the trial centre, or, if all once-weekly 24-hour sampling periods are needed, after discharge on Day 37. EoT examination includes physical examination, vital signs, ECG, safety laboratory, recording of AEs and concomitant therapies.
11. The planned times for admission, discharge, start and end of the urine and faeces collection intervals are approximate. The procedures are to be performed within a time window of +/- 4 hours to the planned time.
12. Subjects are to collect faeces at home within 24-hour intervals before admission to once-weekly in-house collection intervals. Home collection intervals: Days 14-16, 21-23, 28-30, and 35-37. If faeces are collected in the subsequent in-house collection interval, faeces collected at home will be discarded. If no faeces is collected in the subsequent in-house collection interval (no defecation), faeces collected at home will be used instead for analysis.
13. For definition of the individual subject's end of trial, see [Section 6.2.3](#).
14. Subjects will collect a pre-dose faeces sample at home or at the site in specific containers provided by [REDACTED]

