5.2.6.2 Adverse event collection and reporting

5.2.6.2.1 AE collection

Upon enrolment into a trial, the subject's baseline condition is assessed (for instance, by documentation of medical history/ concomitant diagnoses), and relevant changes from baseline are noted subsequently.

Subjects will be required to report spontaneously any AEs as well as the time of onset, end time, and intensity of these events. In addition, each subject will be regularly assessed by the medical staff throughout the clinical trial and whenever the investigator deems necessary. As a minimum, subjects will be questioned for AEs (and concomitant therapies) at the time points indicated in the [Flow Chart](#). Assessment will be made using non-specific questions such as 'How do you feel?'. Specific questions will be asked wherever necessary in order to more precisely describe an AE.

A carefully written record of all AEs shall be kept by the investigator in charge of the trial. Records of AEs shall include data on the time of onset, end time, intensity of the event, and any treatment or action required for the event and its outcome.

The following must be collected and documented on the appropriate CRF(s) by the investigator:

- From signing the informed consent onwards until an individual subject's end of trial
 - All AEs (serious and non-serious) and all AESIs
 - The only exception to this rule are AEs (serious and non-serious) and AESIs in Phase I trials in healthy subjects, when subjects discontinue from the trial due to screening failures prior to administration of any trial medication. In

Proprietary confidential information © 2020 Boehringer Ingelheim International GmbH or one or more of its affiliated companies

these cases, the subjects' data must be collected at trial site but will not be entered in the CRF or trial database and will not be reported in the CTR.

- After the individual subject's end of trial
 - The investigator does not need to actively monitor the subject for AEs but should only report any occurrence of cancer and related SAEs and related AESIs of which the investigator may become aware of by any means of communication, e.g. phone call. Those AEs should, however, not be reported in the CRF.

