7.3.4 Safety analyses

Safety will be analysed based on the assessments described in [Section 2.2.2.2](#). All treated subjects (TS, refer to [Section 7.2](#)) will be included in the safety analysis. Safety analyses will be descriptive in nature and based on BI standards. No hypothesis testing is planned.

For all analyses, the treatment actually administered (= treatment at onset) to the subject will be used (any deviations from the planned treatment will be discussed in the minutes of the Report Planning Meeting).

Treatments will be compared in a descriptive way. Tabulations of frequencies/proportions will be used to evaluate categorical (qualitative) data, and tabulations of descriptive statistics will be used to analyse continuous (quantitative) data.

Measurements (such as vital signs, or laboratory parameters) or AEs will be assigned to treatments (see [Section 4.1](#)) based on the actual treatment at the planned time of the measurement or on the recorded time of AE onset (concept of treatment emergent AEs). Therefore, measurements planned or AEs recorded prior to first intake of trial medication will be assigned to the screening period, those between trial medication intake and discharge from study site (see [Section 1.2.6](#)) will be assigned to the treatment period. Events occurring after discharge from study site but prior to end of trial termination date will be assigned to 'follow-up'. These assignments including the corresponding time intervals will be defined in detail in the TSAP. Note that AEs occurring after the last per protocol contact but entered before final database lock will be reported to Pharmacovigilance only and will not be captured in the trial database.

Additionally, further treatment intervals (analysing treatments) may be defined in the TSAP in order to provide summary statistics for time intervals, such as combined treatments, on-treatment totals, or periods without treatment effects (such as screening and follow-up intervals).

Adverse events will be coded using the Medical Dictionary for Regulatory Activities (MedDRA). Frequency, severity, and causal relationship of AEs will be tabulated by treatment, system organ class, and preferred term. SAEs, AESIs (see [Section 5.2.6.1.4](#)), and other significant AEs (according to ICH E3) will be listed separately.

Previous and concomitant therapies will be presented per treatment group without consideration of time intervals and treatment periods.

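### Do the on-treatment adverse event tables silently narrow the secondary endpoint on drug-related adverse events?

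*SAP*

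**What the plan says.** SAP 5.2.2, repeating Protocol 2.1.3, defines the secondary safety endpoint as "Percentage of subjects with drug related adverse events (AEs) including clinically relevant findings from the physical examination". No time window appears in that sentence. SAP Section 4 says how it will be delivered: "Tables will be provided for disposition, demography and adverse events (including one of the secondary endpoints", with mass balance and PK tables for the remaining primary and secondary endpoints.

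SAP 6.1 divides AEs into screening, on-treatment and follow-up phases. The on-treatment phase runs from administration "until 0:00h on the day after discharge from study site at Day 9". For the AE tables in Section 15.3 of the trial report and the registry displays, "Screening and Follow-up period will not be included in this analysis". For the listings, "screening and follow-up periods will be included and no totals will be provided".

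On the protocol side, Section 5.2.6.2.1 collects AEs "From signing the informed consent onwards until an individual" subject's end of trial. Section 7.3.2 refers the secondary safety endpoint to Section 7.3.4 for its assessment. Section 7.3.4 applies the treatment-emergent concept and assigns onsets from intake to discharge to the treatment period. It continues "Events occurring after discharge from study site but prior to end of trial termination date will be assigned to" follow-up. It also has AEs tabulated by treatment, and hands the detailed definition of the intervals to the SAP.

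**The concern.** Read from the SAP alone, the endpoint and its table do not seem to match. The definition is open-ended and AEs are recorded to the end of trial, yet the table stops at 0:00h on Day 10. SAP Section 4, which exists to list changes in the planned analysis, does not mention the cut-off. SAP 7.5.2 quotes from Protocol 7.3.2 only the sentence on methods, not the one that sends the safety endpoint to Section 7.3.4, so the link is easy to miss.

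The wording on physical examination findings sharpens the doubt. Flow Chart 1, footnote 10, has the "End-of-trial (EoT) examination to be performed after last discharge from the trial centre". If that examination took place on Day 10 or later, a new drug-related finding with onset after the cut-off would be listed but not counted. With so few subjects, one missed case would visibly change a named secondary endpoint that is also reported to the registries.

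**Working it through.** **Which protocol text governs the analysis**

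1. Protocol 2.1.3 names the endpoint and gives no window.
2. Protocol 7.3.2 directs the analysis of this endpoint to Section 7.3.4.
3. Protocol 7.3.4 supplies the window: treatment-emergent attribution by onset, treatment period from intake to discharge, everything later in follow-up. It also names follow-up, with screening, as an example of an interval without treatment effects.
4. Protocol 7.3.4 leaves the exact intervals to the SAP. SAP 6.1 defines them, cites Section 7.3.4, and explains why discharge is used instead of the residual effect period (that period refers to the unlabelled compound).
5. Protocol 5.2.6.2.1 covers what is recorded. Its period starts at consent, before any drug is given, so it cannot also be the period a by-treatment table counts.

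For analysis purposes the endpoint therefore has a time limit, and the protocol set it.

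**Is the SAP window narrower than the protocol's?**

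Inputs: planned dosing on Day 1 at 08:00 = 0 h and planned discharge on Day 9 at 08:00 (Flow Chart 1); residual effect period 7 days (Protocol 1.2.6); cut-off 0:00h on the day after Day 9 discharge, with all subjects discharged on Day 9 (SAP 6.1).

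- Discharge: 8 × 24 = 192 h, which reproduces the Flow Chart's 192:00.
- SAP cut-off, 0:00h on Day 10: 9 × 24 − 8 = 208 h.
- Residual effect period: 7 × 24 = 168 h.
- SAP cut-off minus discharge: 208 − 192 = 16 h.
- SAP cut-off minus residual effect period: 208 − 168 = 40 h.

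Protocol 7.3.4 cross-refers to Section 1.2.6 when it mentions discharge. Whether its treatment period is read as ending at discharge or at the end of the residual effect period, the SAP window covers it.

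**What could fall outside the count**

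- One subject in the percentage: 1/7 = 14.3 points (n = 7, SAP 6.1).
- Shortest follow-up: 0 days, if the end-of-trial examination is on Day 9, which Flow Chart 1, footnote 18, foresees.
- Longest follow-up the visit row allows: 0:00h on Day 10 to 0:00h on Day 39 = 29 days, if that examination is on Day 38.

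The upper end is doubtful. Footnote 10 places the examination after Day 37 only when all weekly collection periods are needed, while SAP 6.1 reports Day 9 discharge for everyone. If that was the final discharge, no weekly visits followed. The documents give no examination dates.

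Phases are assigned by AE onset. A finding noted late but dated on or before Day 9 still counts, and SAP 7.8.5 routes physical examination findings arising after dosing through AE reporting.

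**The case for a change.** The best argument for the concern is that placing an event in a phase is not the same as removing it from an endpoint. Protocol 7.3.4 never says outright that drug-related follow-up AEs leave this percentage, and it permits summary statistics for follow-up intervals if the SAP defines them. The last step is the SAP's. The scheduled post-dose physical examination may fall after the cut-off, and the tables are labelled with the treatment's short label, so a registry reader may not see that the figure is on-treatment only.

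Part of this stands. The endpoint sentence does not repeat its window, and naming the phase in the table title would help. That is missing detail rather than an error. A treatment-emergent analysis tabulated by treatment, with follow-up held as a separate interval, is ordinarily read as counting on-treatment onsets, and SAP 6.1 says so expressly. The permission to summarise follow-up is optional. How the final tables are footnoted cannot be judged either, because SAP 7.8.1 refers to display templates outside the documents. A second percentage from dosing to end of trial would be a reasonable extra, but it is a preference in presentation: in a group of 7, the listings let any reader count later events directly.

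**Conclusion.** The concern does not hold. The restriction applies the protocol's own analysis section for this endpoint, uses an interval the protocol asked the SAP to define, and is stated where that interval is defined. It is not a departure that SAP Section 4 had to list.

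The window of 208 h exceeds planned discharge by 16 h and the residual effect period by 40 h. The possible effect is 14.3 points for each subject whose only drug-related AE began in follow-up, and nil if there was none or if every end-of-trial examination took place on Day 9 with no later onset recorded. Such events remain listed. The endpoint is descriptive and no hypothesis is tested (Protocol 7.2).

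This rests on two assumptions: that Protocol 7.3.4 governs the endpoint, as Protocol 7.3.2 says, and that dosing and discharge kept to the planned 08:00 clock times. A shift of some hours in either would change the margins but not the conclusion, because the cut-off is always the midnight after discharge and so never earlier than discharge itself.
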